6.1.11.1 Examination of Responders

Responder analyses will be conducted for the primary efficacy endpoint and for the secondary endpoints, absolute change from Baseline in non-inflammatory lesion counts at Day 84 and subjects with an IGA score of “clear” or “almost clear” at Day 84 and at least a 2-grade reduction from the Baseline IGA score. Responders are defined as, 80th percentile showing absolute reduction in inflammatory lesions from Baseline. These analyses will be summarized using descriptive statistics. The specific subsets within the responder PP analysis set that will be evaluated include:

- Baseline inflammatory lesion count (< median vs \geq median);
- Baseline non-inflammatory count (< median vs \geq median);
- Baseline total lesion count (< median vs \geq median and < 80th percentile vs \geq 80th percentile);
- Baseline IGA (3 (Moderate) vs 4 (Severe));
- Compliance (percent compliance < median vs \geq median)

6.2 Disposition of Subjects

The number of subjects included in each analysis population (randomized, ITT, safety, PP) will be summarized by treatment group. The number of subjects completed and discontinued (including the reasons for discontinuation) will be summarized for each treatment group.

Subjects who are excluded from an analysis population will be summarized by the reasons for exclusion.

6.3 Protocol Deviations

Protocol deviations will not be entered into the database. Deviations leading to exclusion from analysis populations will be identified and summarized.

6.4 Data Sets Analyzed

6.4.1 Randomized Population

All subjects who are randomized to study treatment will be included in the randomized population and will be analyzed according to the treatment group they were randomized. Listings will be presented for all randomized subjects.

6.4.2 Intent-to-Treat (ITT) Population

All subjects in the randomized population will be included in the ITT population and analyzed according to the randomized treatment group. All efficacy analyses will be presented using the ITT population.

6.4.3 Safety Population

All subjects in the ITT population, who have at least one confirmed dose of study drug, and have at least one post-Baseline assessment will be included in the safety population and analyzed according to the treatment group received. All safety analyses will be performed using the safety population.

6.4.4 Per-Protocol (PP) Population

All subjects in the ITT population who complete the Day 84 visit without noteworthy study protocol violations will be included in the PP population and analyzed according to the treatment group received. The PP population will include subjects in the ITT population who do not meet any of the following criteria:

- Violated the inclusion/exclusion criteria;
- Have taken any interfering concomitant medication;
- Did not complete both IGA and lesion count efficacy assessments at the Day 84 visit;
- Have missed both the Day 28 and Day 56 visits;
- Have not been compliant with the dosing regimen (i.e. subjects must apply 80-120% of the expected applications of study medication during participation in the study);
- Out of visit window at the Day 84 visit by ± 5 days;

Subjects that discontinue from the study due to an AE related to study treatment or documented lack of treatment effect will be included in the PP population. Prior to breaking the blind, other

additional criteria may be added to the list to accommodate for unforeseen events that occurred during the conduct of the trial that result in noteworthy study protocol violations.

All efficacy analyses will be performed on the PP population.

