9.3. Analysis Datasets

This study will be evaluated using 3 analysis sets: intent-to-treat (ITT), per protocol (PP), and safety. Efficacy conclusions will be drawn from the ITT analysis set. The PP analysis set will be used to support the efficacy findings in the ITT analyses. Safety conclusions will be drawn from the safety analysis set.

The ITT analysis set includes all subjects who are randomized and is based on randomized study group, regardless of study drug received. The safety analysis set includes all subjects who are randomized, receive at least 1 confirmed dose of study drug, and have at least 1 post-Baseline assessment. The safety analysis set will be assessed based on study drug received, regardless of group to which subject was randomized. The PP analysis set includes all subjects in the ITT analysis set who complete the Day 84 visit without noteworthy study protocol violations, including compliance with study drug application, Day 84 visit window, and completion of efficacy

evaluations on Day 84. The full definition of the PP population is given in the SAP which will be approved prior to database lock.

Subjects who have a documented lack of treatment effect or who are discontinued from the study due to an AE that was considered by the investigator to be study drug related will be included in the PP analysis set. Specific criteria for identifying the PP analysis set will be determined prior to breaking the blind.

Vehicle QD and Vehicle BID groups may be combined for analyses.

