6.1.3 Visit Windowing

Data will be summarized based on nominal visit indications with the exception of data captured at early termination and unscheduled visits. Data from early termination and unscheduled visits will be summarized based on mapped visit values. The analysis windows for early termination and unscheduled visits are presented in the following table.

Analysis Windows

Scheduled Visit	Target Study Day	Window (Days)
Day 14	15	9 to 21
Day 28	29	22 to 42
Day 56	57	43 to 70
Day 84	85	71 to 98

Data collected at early termination and unscheduled visits prior to study day 9 will not be analyzed, with the exception of those identified as baseline values. Data collected at early termination and unscheduled visits after study day 98 will not be included in analyses.

The definition for the study day included in each study window is defined as below:

Study Day prior to Day 1 = Visit Date – Day 1 Date

Study Day on or after Day 1 = Visit Date – Day 1 Date + 1

If an assessment's mapped visit is a visit at which the subject has data from a scheduled visit present, or if no analyses are planned for the assessment at the mapped visit, the data collected at the early termination or unscheduled visit will not be included in analyses.

In the event of multiple values from unscheduled or early termination assessments within an analysis window, the value closest to the scheduled visit target study day will be used for analyses. If two values tie as closest to the time point (for example, one value is before and the other value is after the time point), then the later value will be selected.

Data collected at all visits will be included in the data listings with visit presented as reported by the site.

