6.1.5 Handling of Dropouts or Missing Data

All efforts will be made to minimize the occurrence of missing data. It is not expected that dropout rates will differ between groups. Therefore, the primary method of handling missing efficacy data in the ITT analysis set will be based on last observation carried forward (LOCF). Summary of efficacy and pharmacology variables for the PP subjects will be based on available data. No imputation will be done for non-efficacy related variables.

If a partial date is reported where the day is missing, then the day will be imputed as the first day of the month unless the month is the same month as the first application of study drug then the day will be that of first application with the month and year remaining the same. If a partial date is reported where the month is missing, then the month will be imputed to January unless the year is the same year as the first application of study drug then the month will be that of first application with the year remaining the same. If a partial date where both the day and month is missing, follow details as stated previously.

Missing AE start dates will be imputed using partial date imputation rules as previously described in this Section.

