SD	xx.xx	xx.xx	xx.xx	xx.xx	xx.xx	xx.xx	
Median	xx.x	xx.x	xx.x	xx.x	xx.x	xx.x	
Min., Max.	xx, xx	xx, xx	xx, xx	xx, xx	xx, xx	xx, xx	
LSMean ^a			xx.x	xx.x	xx.x	xx.x	0.xxxx ^b
LSSD ^a			xx.xx	xx.xx	xx.xx	xx.xx	
Unranked P-value vs. Combined Vehicle ^a				0.xxxx	0.xxxx	0.xxxx	
Ranked P-value vs. Combined Vehicle ^c				0.xxxx	0.xxxx	0.xxxx	

^a Least squares mean, standard deviation, and contrast p-values from an analysis of covariance with factors of treatment group (vehicle treatment groups included as single combined treatment group) and corresponding baseline lesion count as the covariate.

^b Skewness test is based on methods presented by J.H. Zar (1984).

^c Contrast p-values from a ranked analysis of covariance with factors of treatment group (vehicle treatment groups included as single combined treatment group) and corresponding baseline lesion count as the covariate.

Note: Missing values imputed using LOCF.

SOURCE: USERNAME\SPONSOR\PROJECT\JOBNAME (DATE,TIME)

Repeat Table 14.2.1.1 for the following:

Table 14.2.1.2: Primary Efficacy Endpoint: Summary of Absolute Change from Baseline in Inflammatory Lesion Count at Day 84 (PP Population)

Programming note: replace last footnote with:

Note: No imputations were made for missing data.

Table 14.2.1.3: Sensitivity Analysis of Primary Efficacy Endpoint: Summary of Absolute Change from Baseline in Inflammatory Lesion Count at Day 84 (ITT Population)

Repeated Measures Analysis on Observed Data	Vehicle QD (N=xx)	Vehicle BID (N=xx)	Vehicle Combined (N=xx)	BTX 1503 5% BID (N=xx)	BTX 1503 5% QD (N=xx)	BTX 1503 2.5% QD (N=xx)
Change from Baseline in Inflammatory Lesion Counts						
n	xx	xx	xx	xx	xx	xx
Mean	xx.x	xx.x	xx.x	xx.x	xx.x	xx.x
SD	xx.xx	xx.xx	xx.xx	xx.xx	xx.xx	xx.xx
Median	xx.x	xx.x	xx.x	xx.x	xx.x	xx.x
Min., Max.	xx, xx	xx, xx	xx, xx	xx, xx	xx, xx	xx, xx
LSMean ^a			xx.x	xx.x	xx.x	xx.x
LSSD ^a			xx.xx	xx.xx	xx.xx	xx.xx
P-value vs. Combined Vehicle ^a				0.xxxx	0.xxxx	0.xxxx

^a Least squares mean, standard deviation, and contrast p-values from a repeated measures analysis of covariance with factors of treatment group (vehicle treatment groups included as single combined treatment group), visit, treatment by visit interaction, and corresponding baseline lesion count as the covariate. Note: No imputations were made for missing data.

SOURCE: USERNAME\SPONSOR\PROJECT\JOBNAME (DATE,TIME)

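### Dropouts that the SAP admits to the per-protocol set for a related AE or lack of effect drop out of its Day 84 results unless they have a Day 84 value

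*SAP*

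**What the plan says.** SAP 6.4.4 starts from ITT subjects who complete Day 84 and removes anyone meeting a listed criterion. Two of those criteria are "Did not complete both IGA and lesion count efficacy assessments at the Day 84 visit" and "Have missed both the Day 28 and Day 56 visits"; others cover dosing compliance and the Day 84 visit window. After the list, it states that subjects who discontinue "due to an AE related to study treatment or documented lack of treatment effect will be included in the PP population". Protocol 9.3 has the same pairing: a completer rule, then PP membership for "Subjects who have a documented lack of treatment effect or who are discontinued from the study due to an AE" that the investigator judged drug-related.

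SAP 6.1.9 defines PP again, by Day 84 completion only and without the exception. Table 14.0.2 lists a missed Day 84 IGA or lesion count among the reasons for PP exclusion.

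On missing data, SAP 6.1.5 applies LOCF to ITT and says of PP: "Summary of efficacy and pharmacology variables for the PP subjects will be based on available data". The programming notes for the PP tables replace the LOCF footnote with "Note: No imputations were made for missing data", both for lesion counts (Table 14.2.1.2) and for dichotomized IGA (Table 14.2.2.3.2). The repeated-measures sensitivity analysis in 6.9 is on ITT only.

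On timing, SAP 6.1.3 uses nominal visits for scheduled data, but "Data from early termination and unscheduled visits will be summarized based on mapped visit values", and "Data collected at early termination and unscheduled visits prior to study day 9 will not be analyzed" unless they serve as Baseline.

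**The concern.** The inclusion sentence admits to PP the subjects in whom treatment failed on tolerability or efficacy. Membership alone does not put them into a Day 84 comparison. That needs a Day 84 value, and the PP rules neither impute one nor borrow from earlier visits. Someone who left in week 5 and did not come back can be in the PP set and still be absent from its Day 84 ANCOVA, logistic regression, subgroup and responder tables. The lesion-count shells would show this as n below N. The IGA shells have no n row, so there the denominator would not be visible.

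PP is the named support for the ITT result. It is the set on which the SAP places its subgroup and responder tables (6.1.11, 6.1.11.1), and 6.1.9 relies on it for a clearer view of dose-response. If related-AE and lack-of-effect failures are missing at Day 84, those tables describe something closer to completers than the stated definition suggests.

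**Working it through.** The plan gives no figure for this, so the check follows the rules and then sizes the effect with stated assumptions.

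**Where an early exit lands (SAP 6.1.3).** For data recorded as early-termination or unscheduled:

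- before study day 9: not analysed;
- days 9–21: Day 14;
- days 22–42: Day 28;
- days 43–70: Day 56;
- days 71–98: Day 84;
- after day 98: not analysed.

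An exit visit so recorded up to study day 70 gives no Day 84 value. That span is 70 of the 84 treatment days, 70/84 = 83%. This counts calendar days. It is not an expected share of dropouts, because the documents do not say when subjects leave or how many return.

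**What an included dropout without a Day 84 value contributes.** PP N; PP demographic and baseline tables (6.5); PP analyses at Day 14, 28 and 56 for which data exist (6.8.3.1, 6.8.3.2). Not the PP Day 84 ANCOVA, logistic, subgroup or responder results.

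**Size, lesion counts.** Let p be the share of an arm's PP set that are such dropouts, and g the gap between the mean reduction in subjects with a Day 84 value and in these dropouts. Leaving the dropouts out raises the arm's mean reduction by p × g, so the between-arm effect is p1 × g1 − p0 × g0. It is zero only if the two products are equal. Assumed ranges: p 0–5%, g 8–12 lesions, in each arm.

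- Extremes: 0.05 × 12 − 0 = +0.6, and −0.6 with the arms reversed.
- Equal 5% rates, gaps of 12 and 8: 0.6 − 0.4 = 0.2.

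**Size, IGA.** Assume 10–30% success among subjects with a Day 84 value and no successes among the missing.

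- Extremes: 0.05 × 30 = 1.5 points, so −1.5 to +1.5.
- Equal 5% rates, success of 30% and 10%: 1.5 − 0.5 = 1.0 point.

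**Against sampling error.** With 90 per active arm, 45 + 45 = 90 in combined vehicle, and an assumed SD of 10–14, SE = SD × √(2/90).

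- SD 10: SE 1.49, and 0.6/1.49 = 0.40.
- SD 14: SE 2.09, and 0.6/2.09 = 0.29.

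The effect is proportional to p, so a larger share would raise it in proportion.

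**Day 84 assessments after withdrawal.** Protocol 5.3.1 seeks the Day 84 assessments from withdrawn subjects, and Table 3 note c does so whenever possible. Protocol 7.3.7 describes the attempt only for terminations for reasons other than an AE. For related-AE dropouts these passages do not agree.

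**The case against.** A general rule followed by a named exception is not a contradiction, and the blinded evaluability review before hard lock can settle who is in PP. That stands: a reader might infer that PP membership is left undetermined, and the documents do not support so strong a reading. What is missing is the list of waived criteria, and the review cannot supply a Day 84 value.

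A reader might also infer that these subjects add nothing to PP, or that every exit visit up to day 70 is lost. Neither follows. They contribute to baseline and earlier-visit tables, and an exit assessment recorded under the nominal Day 84 visit would be used as such under 6.1.3. Note c attaches to the Day 84 column of Table 3, so this may happen.

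Nor does the 80% compliance rule necessarily exclude a dropout who returns at Day 84. It could do so only if participation were counted to the return visit and the exception did not waive the rule. SAP 6.10.1 counts applications expected while enrolled, and Protocol 5.3.1 ends enrollment at withdrawal.

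An as-observed PP analysis beside an ITT LOCF analysis is a legitimate choice, and ITT already carries these dropouts. The subgroup consequence also depends partly on a separate difference: Protocol 9.4.4 places subset analyses in ITT, the SAP in PP. Finally, a related-AE dropout is not necessarily an efficacy failure, so the IGA range is an upper bound. All of this limits the size of the point. It does not change the fact that the plan admits these failures and then gives them no Day 84 outcome.

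**Conclusion.** The point holds in limited form. As written, the inclusion of related-AE and lack-of-effect dropouts does not reach the PP Day 84 results unless the subject has a nominal or mapped Day 84 value. The ITT/LOCF analysis is unaffected, so the primary result is not called into question. PP is supportive, all tests are exploratory without Type I adjustment, and the subgroup and responder tables are descriptive.

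The likely effect is small: at most about 0.6 lesions or 1.5 percentage points between arms, with the lesion figure at 0.3–0.4 of a standard error. Every rate, gap and SD behind those figures is assumed. The change should be made because it is cheap and because deciding after unblinding how treatment failures count would be a data-informed choice.

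**What to change.** - **SAP 6.4.4:** state that the exception waives the Day 84 completion, assessment and window criteria and the missed Day 28/Day 56 criterion. Align 6.1.9 and Table 14.0.2.
- **SAP 6.1.5 and the PP Day 84 table notes:** apply the existing ITT LOCF rule to these subjects' missing Day 84 lesion counts and IGA, and leave other PP subjects as observed. State before unblinding what is done when no analysable post-Baseline value exists; 6.1.5 does not say whether Baseline is carried forward. Show the as-observed PP result beside it.
- **SAP 6.10.1:** state that expected applications for these subjects end at withdrawal, consistent with Protocol 5.3.1.
- **Protocol 5.3.1, 7.3.7 and Table 3 note c:** these differ on Day 84 assessments after an AE withdrawal and must be reconciled.

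Deleting the inclusion sentence from the SAP instead would depart from Protocol 9.3.

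The cost is wording in four SAP sections and one table, a footnote in the PP shells, a derivation flag and an as-observed copy of the PP Day 84 tables. The downside is that PP moves slightly closer to ITT and may look slightly less favourable.

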6.5 Demographic and Other Baseline Characteristics

All demographic and Baseline summaries will be done on the ITT, PP, and safety populations.

Sex, race, and ethnicity will be summarized by counts and percentages. Age, height (cm), and weight (kg) will be summarized with descriptive statistics.

Tobacco and alcohol history will be summarized with counts and percentages. Baseline IGA and inflammatory and non-inflammatory lesion counts will be summarized with descriptive statistics.

Medical histories will be coded using the MedDRA dictionary and presented in a by-subject listing.

6.6 Prior and Concomitant Medications

Concomitant medications will be coded to preferred name and Anatomical Therapeutic Chemical (ATC) classification of ingredients using the World Health Organization (WHO) Drug dictionary (WHO-DDE).

Counts and percentages will be provided to summarize the use of concomitant medications other than the study drug reported throughout the study. The number and percent of subjects who took other therapy will be shown by ATC level 2 term and preferred name. Medications which start prior to first application will be considered prior medications. Ongoing medications and medications ending after the date of first application will be considered concomitant medications. Incomplete start and end dates which could be either prior to first application or after first application will be considered prior to first application.

A by-subject listing of all prior and concomitant medications will be presented.

6.7 Concomitant Antibiotic Therapies

Concomitant antibiotic therapies will be determined by the sponsor prior to database lock.

Counts and percentages will be provided to summarize the use of concomitant antibiotic therapies reported throughout the study. The number and percent of subjects who took concomitant antibiotic therapies will be shown by ATC level 2 term and preferred name.

A by-subject listing of all concomitant antibiotic therapies will be presented.

6.8 Analysis of Efficacy

The efficacy analyses will be performed using the ITT (primary) and PP (supportive) analysis sets. The lesion count and IGA analyses will employ the methods for handling missing data as described by Section 6.1.5. Lesion count and IGA data will also be shown in by-subject listings.

6.8.1 Primary Efficacy Analysis

Absolute change from Baseline to Day 84 in inflammatory lesion counts will be analyzed using either parametric or non-parametric methods consistent with the statistical assumptions required to support the analyses. Specifically, the tests of superiority will be based on an ANCOVA with factors of treatment (with the vehicle treatment groups combined) and the respective Baseline lesion count as a covariate, or on ranked data submitted to an ANCOVA with factors of treatment and the respective Baseline lesion count as a covariate.

A skewness test, based on the methods presented by J.H. Zar (1984), will be applied to the residuals resulting from an ANCOVA. A two-sided p-value for the skewness test significant at 0.01 will imply the use of the non-parametric method. If a parametric analysis is indicated, the results of the parametric analysis will be considered the primary analysis. Should a non-parametric analysis be indicated, the absolute changes in inflammatory lesions will be rank transformed prior to submitting them to the ANCOVA. Results of the rank-transformed analyses then will be considered the primary analysis; however, results of the non-ranked transformed analyses will also be presented.

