Descriptive statistics (including mean, median, standard deviation [SD], minimum, and maximum, unless otherwise stated) will be presented for the following parameters by study group using both the ITT and PP analysis sets:

- Inflammatory, non-inflammatory, and total lesion counts at Baseline, Day 14, Day 28, Day 56, and Day 84,
- Absolute and percent change from Baseline in inflammatory, non-inflammatory, and total lesion counts at study Day 14, Day 28, Day 56, and Day 84,
- IGA scores and frequency and percent distribution of the dichotomized IGA at study Day 14, Day 28, Day 56, and Day 84.

This Phase 2 study is designed to identify the response to two different dosing frequencies and two concentrations of BTX 1503. Statistical tests applied to the outcomes will be exploratory. No adjustments for Type 1 error will occur.

[figure not shown]
The change from Baseline in lesion counts (inflammatory and non-inflammatory; separate and combined, and total) at Days 14, 28, 56, and 84 will be analyzed using ANCOVA with Baseline lesion count and treatment as covariates. Success on IGA defined as a score of clear or almost clear and/or at least a 2-grade improvement from Baseline at Day 14, Day 28, Day 56, and Day 84 will be analyzed using logistic regression, adjusting for Baseline IGA.

Safety Analyses:

All subjects who receive at least one confirmed dose of study drug and have at least one post-Baseline assessment will be included in the safety analyses. Safety analyses will include summaries of treatment-emergent adverse events (TEAEs), serious AEs (SAEs), and changes in laboratory assessments. TEAEs and SAEs will be summarized by treatment group, the number of subjects reporting events, system organ class, preferred term, severity, relationship to study drug, and

| | |

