- The change from baseline in the IGA scores and Day 84,
- The absolute and percent change from Baseline in inflammatory, non-inflammatory and total lesion counts at Day 14, Day 28 and Day 56.
- The proportion of subjects with at least a 2-grade reduction from the Baseline IGA score at Day 14, Day 28 and Day 56, and
- The proportion of subjects with an IGA score of “clear” or “almost clear” at Day 14, Day 28 and Day 56,
- The proportion of subjects with an IGA score of “clear” or “almost clear” at Day 14, Day 28 and Day 56 and at least a 2-grade reduction from the Baseline IGA score.
- The change from Baseline in the Acne-QoL at Day 84, and
- Subject’s assessment of the change in their acne from baseline to Day 84 (PRO).

Tests of superiority for the primary and secondary endpoints of absolute change from Baseline in lesion counts will be based on either parametric or nonparametric methods consistent with the statistical assumptions required to support the analyses. Specifically, the tests of superiority will be based on an ANCOVA with factors of treatment and the respective Baseline lesion count as covariates, or on ranked data submitted to an ANCOVA with factors of treatment, analysis center, and the respective Baseline lesion count as a covariate.

Data will be reviewed for skewedness (details in the SAP). If a parametric analysis is indicated, the results of the parametric analysis will be considered the primary analysis. If a nonparametric analysis is indicated, the absolute or percent changes in inflammatory lesion counts will be rank-transformed prior to submitting them to the ANCOVA. Results of the rank-transformed analyses

will then be considered the primary analysis; results of the nonrank-transformed analyses will be also presented.

The dichotomized IGA will be analyzed with logistic regression, adjusting for baseline IGA and site. Pairwise tests will be conducted comparing the treated groups to vehicle. The lesion count and IGA analyses employ the methods for handling missing data described in [Section 9.4.9](#).

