9.6. Measures to Minimize Bias

9.6.1. Enrollment/Randomization/Masking Procedures

A randomization code will be prepared by an unblinded statistician at the CRO. This statistician will be the only person aware of the randomization code. Randomization will be 2:2:2:1:1 (90 subjects in each active group and 45 in each vehicle group) and done by site. Once a subject is deemed eligible to enroll, randomization will occur. The site will contact the IVRS/IWRS to receive the kit number to be used for that subject throughout the study.

Study drug, active or vehicle, will be labelled identically except for the kit number and bottle number. Study drug pumps will contain approximately 39 mL for BID dosing groups and approximately 21 mL for QD dosing groups. There is no double-dummy in this study for BID vs QD dosing, so knowledge of volumes (during study drug accountability) will not unmask treatment groups (active vs vehicle). The vehicle study drug is indistinguishable from the active study drug.

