4.1.2 Method of Assigning Subjects to Treatment Groups

A randomization schedule will be generated by a member in the QST Consultations, Ltd. (QST) Statistical Services department who is not associated with the conduct or analysis of the study, using a validated system. The randomization list will not be stratified, but stratification by site will be accomplished within the Interactive Web-based Randomization System (IWRS).

Once a subject is deemed eligible to enroll, randomization will occur using an IWRS. The IWRS will assign a study drug kit number based on a predetermined randomization schedule. The kit number will be recorded in the electronic case report form (eCRF). Randomization will be 2:2:2:1:1 (90 subjects in each active group and 45 in each vehicle group) and done by site.

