6.1.4 Adjustments for Covariates

Baseline lesion count will be a covariate for the efficacy endpoints for acne lesion counts. No other covariates are planned to be used in the analyses for this study.

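### The parametric primary ANCOVA leaves out site, the randomisation stratum; if sites differ in Baseline-adjusted change, its standard errors are too wide and its tests conservative

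*SAP*

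**What the plan says.** Protocol 9.6.1 states: "Randomization will be 2:2:2:1:1 (90 subjects in each active group and 45 in each vehicle group) and done by site". SAP 4.1.2 repeats this and names the mechanism: "stratification by site will be accomplished within the Interactive Web-based Randomization System (IWRS"). Site is therefore the stratification factor in both documents.

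The parametric primary model does not contain it:

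- SAP 6.8.1: "an ANCOVA with factors of treatment (with the vehicle treatment groups combined) and the respective Baseline lesion count as a covariate".
- SAP 6.1.4, after naming Baseline lesion count: "No other covariates are planned to be used in the analyses for this study".
- Protocol 9.4.3: "the tests of superiority will be based on an ANCOVA with factors of treatment and the respective Baseline lesion count as covariates".
- Protocol section 1: change in lesion counts "will be analyzed using ANCOVA with Baseline lesion count and treatment as covariates".

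In the same sentence of protocol 9.4.3, the ranked alternative to that ANCOVA has analysis center as a factor. The SAP's ranked model does not. The skewness test in SAP 6.8.1 decides which of the two models is primary. Neither document says why site is left out of the parametric one.

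**The concern.** Allocation within site balances the arms on site, so the treatment contrast is nearly free of between-site variance. A model without site still leaves that variance in the residual, and the reported standard error is built from the residual. If sites differ in outcome after Baseline adjustment, the standard error overstates the uncertainty of the contrast, intervals are too long and p-values too large.

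Site differences are plausible. Lesions are counted by each site's investigator or designee (protocol 7.1), and the sites are in the United States and Australia (SAP 6.1.7). The same ANCOVA serves the secondary lesion-count endpoints (SAP 6.8.2.1) and the visit-wise analyses (6.8.3.1), and the repeated-measures model in 6.9 also omits site.

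This is separate from the protocol-SAP differences on the ranked ANCOVA and the IGA logistic model. Restoring the protocol's wording there would still leave the parametric primary model without site.

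**Working it through.** **Plan's own figures.** 360 x 2/8 = 90 per active arm and 360 x 1/8 = 45 per vehicle arm; 3 x 90 + 2 x 45 = 360. Each primary contrast is 90 versus 45 + 45 = 90. No power, effect size, SD or significance level for treatment tests accompanies these sizes (protocol 9.5, SAP section 7), so there is no power figure to reproduce.

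**Assumptions.** Two-sided 0.05; residual SD 1 after Baseline adjustment; no dropout; standardised effect (1.960 + 0.842) x sqrt(2/90) = 0.418, which gives 80% power at ICC 0. ICC is varied because the documents give no value.

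**Analytic result**, with complete balance within sites and no cost for estimating site effects:

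- Reported over true standard error, model without site: 1/sqrt(1 - ICC).
- True two-sided size without site: 2 x (1 - Phi(1.96/sqrt(1 - ICC))).
- Power without site: Phi((0.418 x sqrt(45) - 1.96)/sqrt(1 - ICC)).
- Power with site: Phi(0.418 x sqrt(45)/sqrt(1 - ICC) - 1.96).

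| ICC | SE ratio | True size | Power without site | Power with site | Gain (points) |
|---|---|---|---|---|---|
| 0 | 1.000 | 5.0% | 80.0% | 80.0% | 0 |
| 0.02 | 1.010 | 4.8% | 80.2% | 80.8% | 0.6 |
| 0.05 | 1.026 | 4.4% | 80.6% | 82.0% | 1.4 |
| 0.10 | 1.054 | 3.9% | 81.3% | 84.0% | 2.7 |
| 0.20 | 1.118 | 2.8% | 82.7% | 87.9% | 5.2 |

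**Simulation with the cost of site effects included.** 360 subjects in unequal sites, permuted blocks of 8 within site, vehicles combined, 3000 trials per cell (standard error about 0.7 points per power figure). Entries are power in %, without / with site. The pooled rows merge sites of fewer than 8 subjects within country and assume a 70/30 split of sites between the countries.

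| Sites | ICC 0 | ICC 0.05 | ICC 0.10 | ICC 0.20 |
|---|---|---|---|---|
| 15, unpooled | 79.9 / 79.3 | 80.4 / 81.4 | 80.8 / 83.2 | 82.2 / 86.8 |
| 30, unpooled | 80.0 / 79.4 | 80.9 / 81.5 | 79.7 / 81.6 | 83.1 / 87.7 |
| 60, unpooled | 79.0 / 76.4 | 81.3 / 79.6 | 81.3 / 82.2 | 82.0 / 85.0 |
| 20, pooled | 78.4 / 78.1 | 79.6 / 80.1 | 80.7 / 83.5 | 82.4 / 87.4 |
| 36, pooled | 80.0 / 79.5 | 80.1 / 80.7 | 82.5 / 84.8 | 82.5 / 86.8 |
| 60, pooled | 78.6 / 78.4 | 79.1 / 79.5 | 79.4 / 81.1 | 82.1 / 85.1 |

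A second pooled run (20, 36 and 60 sites) cost at most 0.3 points at ICC 0 and gained 0.3 to 1.6 points at 0.05, 1 to 2.5 at 0.10 and 4 to 5 at 0.20. A separate run with 20 or 36 sites gave 0.88 with site against 0.82 without at ICC 0.20, the upper end of the range. In the unpooled runs at ICC 0.20, the size of the test without site was 3.0% to 3.5%.

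The 60-site unpooled row shows when adjustment backfires. At 360/60 = 6 subjects per site, the average site does not complete one cycle of the ratio (2 + 2 + 2 + 1 + 1 = 8), so site effects absorb treatment information.

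**The case against.** The case for leaving the model alone has real content.

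- *The effect is conditional.* A reader might infer that power is simply being thrown away. The documents do not support that: they give no between-site variance and no number of sites. At ICC 0 nothing is lost, and with many sparse unpooled sites the model without site can be the more powerful one. This stands, and the point is limited accordingly.
- *The rater argument is weaker than it looks.* A constant offset in one site's counts affects Baseline and Day 84 alike, so it partly cancels in a change score adjusted for Baseline, and protocol 7.1 requires documented training in counting. This stands as a reason not to presume a large ICC. It does not rule out sites differing in response.
- *There is no planned power to fall short of.* The sample size is not power-based, tests are exploratory without type I error adjustment, and protocol 9.2 says a non-significant result would not mean the study had failed. This stands: no shortfall against the plan can be shown.
- *False positives.* A reader might take an ignored stratum to mean an inflated type I error. The error runs the other way.
- *Phase 3 sample size.* SAP 6.1.8 says the tests will help set it. The residual SD from this model would overstate the requirement only if Phase 3 is analysed with site adjustment. For a Phase 3 analysed without site it is the matching input, and the documents do not say which is intended.
- *The cost of adjusting.* The loss with 60 sites arises with unpooled fixed effects. With small sites pooled, the simulated cost at ICC 0 was at most about half a point, within simulation error.

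**Conclusion.** The point holds in conditional form. Randomisation is stratified by site, both documents leave site out of the parametric primary ANCOVA without giving a reason, and the protocol puts center in the ranked version of the same test. If sites differ in Baseline-adjusted change, standard errors are too wide by about 1/sqrt(1 - ICC): 2.6%, 5.4% and 11.8% at ICC 0.05, 0.10 and 0.20. The tests are then conservative.

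The power given up is nil at ICC 0, about 1 point at 0.05, 1 to 3 points at 0.10 and 3 to 6 points at 0.20. These sizes rest on assumed values for the ICC, number and size of sites, block size, significance level and effect, and on allocation being balanced within site as the IWRS stratification implies. Nothing in the documents shows which ICC applies. This is a cheap improvement in precision, not a threat to the validity of a positive result.

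**What to change.** Before unblinding:

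1. In SAP 6.1.4 and 6.8.1, add site (analysis center) as a factor in the ANCOVA. Apply it to the primary endpoint, the other lesion-count endpoints (6.8.2.1, 6.8.3.1) and the repeated-measures model in 6.9, and update the table footnotes.
2. Pre-specify how small sites are handled: for example, pool sites with fewer than 8 subjects within country, 8 being one full cycle of 2:2:2:1:1, or fit site as a random effect. Neither document states a block size, so the threshold should be checked against the actual one.
3. Record this in SAP section 8, which now declares no changes. The protocol specifies the same parametric model without site, so this is a departure from it.
4. If the sponsor prefers to leave site out, give the reason in 6.1.4.

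The cost is SAP wording and some degrees of freedom. The present model leaves 360 - 5 = 355; 20 site levels would use 19 of these. Unpooled fixed effects should be avoided if sites are many and sparse, since at about 60 sites they could cost 2 to 3 points of power at low ICC.
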